10.4.2 Quality Assurance

Independent study audit(s) and/or inspection(s) may take place at any time during or after the study. The independent audit/inspection can be carried by the Quality Assurance (QA) of the CRO, the independent QA [REDACTED] At all times, the confidentiality of patient-related documents will be maintained.

11. PREMATURE TERMINATION OF THE WHOLE STUDY

The whole study may be discontinued at the discretion of the Sponsor in the event of any of the following:

- New information leading to unfavorable risk-benefit judgement of the investigational products due to:
 - Occurrence of clinically significant unknown AEs or unexpectedly high intensity or incidence of known AEs
 - New evidence of unfavorable safety or efficacy findings (from clinical or non-clinical examinations, e.g., toxicology)
- The Sponsors decision that continuation of the study is unjustifiable for medical or ethical reasons
- Discontinuation of development of the IMP

Competent Authorities and IRB/IECs will be informed about the discontinuation of the study in accordance with applicable regulations.

12. END OF CLINICAL TRIAL AND ARCHIVING

The clinical study will end with the collection and analysis of study data and the issue of the clinical study report. All essential documents will be archived by the Sponsor according to the relevant SOP.

12.1 ARCHIVING OF ELECTRONIC DOCUMENTATION/DATA

As described in section 5.5, duplicate electronic media such as CDs/DVDs (1 for routine access and 1 for back-up) containing the patient data in PDF format (i.e., eCRFs) for each site will be prepared by the Sponsor or a delegate for archiving purposes. The electronic media, of not re-printable type, will be appropriately labelled recording the files/data included. The files should contain at least the eData copy clearly reporting the system name, study code and the eCRF version used; for eCRF data also the electronic signature and the associated audit trails have to be included. The Investigator should verify whether the provided electronic media represent a complete copy of eCRFs generated during the study. The Investigator has to confirm the receipt and correctness of the material by signing a dedicate form provided by the Sponsor, the signed form has to be collected and archived in the TMF. Investigators will be also responsible for electronic media refreshment approximately every 7 years to ensure long term archiving of files/data. Two copies of the same electronic media prepared for the sites or cumulative electronic media with the same content will be archived by the Sponsor and refreshed approximately every 7 years to ensure long term archiving of files/data. In addition the sponsor is responsible to create 2 electronic media (1 for routine access and 1 for back-up) containing an integrated SAS database with all study data (e.g., eCRF, central laboratory), with appropriate refreshment procedures.

13. APPENDICES

13.1 APPENDIX I: Contraceptive Guidance and Woman of Childbearing Potential

Definitions

Woman of Childbearing Potential (WOCBP)

A woman is considered fertile following menarche and until becoming postmenopausal unless permanently sterile. Permanent sterilization methods include hysterectomy, bilateral salpingectomy, and bilateral oophorectomy.

Women in the following categories are not considered WOCBP

- Premenopausal female with 1 of the following:
 - Documented hysterectomy
 - Documented bilateral salpingectomy
 - Documented bilateral oophorectomy

Note: Documentation can come from the site personnel's: review of participant's medical records, medical examination, or medical history interview.

- Premenarchal
- Postmenopausal female
 - Females who are postmenopausal (age-related amenorrhea \geq 12 consecutive months and increased follicle-stimulating hormone [FSH] $>$ 40 mIU/mL), or who have undergone hysterectomy or bilateral oophorectomy are exempt from pregnancy testing. If necessary to confirm postmenopausal status, an FSH will be drawn at Screening.
 - Females on HRT and whose menopausal status is in doubt will be required to use one of the non-hormonal highly effective contraception methods if they wish to continue their HRT during the study. Otherwise, they must discontinue HRT to allow confirmation of postmenopausal status before study enrollment.

Contraceptive Guidance

| Highly Effective Contraceptive Methods That Are User Dependent | |
|--|--|
| Failure rate of <1% per year when used consistently and correctly ^a . | |
| Combined (estrogen- and progestogen-containing) hormonal contraception associated with inhibition of ovulation ^b : 
▪ Oral▪ Intravaginal▪ Transdermal | Progestogen-only hormonal contraception associated with inhibition of ovulation ^b : 
▪ Oral▪ Injectable |
| Highly Effective Contraceptive Methods That Are User Independent | |
| 
▪ Implantable progestogen-only hormonal contraception associated with inhibition of ovulation^b▪ Intrauterine device (IUD)▪ Intrauterine hormone-releasing system (IUS)▪ Bilateral tubal occlusion▪ Vasectomized partner (A vasectomized partner is a highly effective contraception method provided that the partner is the sole male sexual partner of the WOCBP and the absence of sperm has been confirmed. If not, an additional highly effective method of contraception should be used.)▪ Sexual abstinence (Sexual abstinence is considered a highly effective method only if defined as refraining from heterosexual intercourse during the entire period of risk associated with the study drug. The reliability of sexual abstinence needs to be evaluated in relation to the duration of the study and the preferred and usual lifestyle of the participant.) | |
| Notes: | |

[figure not shown]
a) Typical use failure rates may differ from those when used consistently and correctly. Use should be consistent with local regulations regarding the use of contraceptive methods for participants participating in clinical studies.

[figure not shown]
b) Hormonal contraception may be susceptible to interaction with the study drug, which may reduce the efficacy of the contraceptive method or susceptible to a clinically relevant interaction with contraceptive steroids (observed or suspected). In this cases, two highly effective methods of contraception should be utilized during the treatment period and for at least 2 months [corresponding to time needed to eliminate study treatment plus 30 days for study treatments with genotoxic potential] after the last dose of study treatment

[figure not shown]
Barrier Methods

- Male or female condom without spermicide
- Cap, diaphragm or sponge with spermicide

[figure not shown]
13.2 APPENDIX II: Tumor Lysis Syndrome Manual for Investigators

[figure not shown]

[figure not shown]

Keratopathy

1. INTRODUCTION

The purpose of this document is to provide further details about the statistical analysis methods specified in study protocol for the Phase I Dose Escalation Study of MEN1309, a CD205 Antibody-Drug Conjugate, in Patients with CD205-Positive Metastatic Solid Tumors and Non-Hodgkin Lymphoma.

The study is sponsored by Menarini Ricerche S.p.A

MEN1309 solution for infusion. MEN1309 will be administered by a 3-hour intravenous (IV) infusion on Day 1 of a 21-day cycle.

In Step 1 (investigation in Solid Tumors), MEN1309 cohort ascending doses start from 0.05 mg/kg up to 3.36 mg/kg. Study drug is given until objective disease progression is documented or another criterion for discontinuation [i.e., protocol violation, a dose-limiting toxicity (DLT), a serious adverse event (SAE), a patient receives other treatment, pregnancy, or withdrawal of consent] is met. Once the maximum tolerated dose (MTD) is determined in solid tumors, patients with locally advanced and metastatic triple negative breast cancer (TNBC) will be enrolled aiming to administer MEN1309 to 25 patients at the MTD (Expansion Phase).

In Step 2 (investigation in Non-Hodgkin's Lymphoma-NHL), escalating dose levels is based upon experience gained during Step 1 solid tumors, i.e. Step 2 is intended to run in parallel with Step 1 but at a lower dose level, so that the cohorts of patients with NHL in Step 2 cannot exceed at any time the doses tested in solid tumors during the dose escalation.

MEN1309-01 cohorts potentially run in parallel at the same dose level only at the MTD. By the end of the study one patient has been treated at 0.08 mg/Kg.

At the time Protocol Version 3.0 was implemented, the dose cohort of 1.60 mg/kg was successfully completed in Step 1, therefore the dose escalation in Step 2 started at 0.80 mg/kg. In Step 2, study drug will be given until objective disease progression is documented or until any other criterion for discontinuation is met, for a maximum number of 8 cycles. Beyond the 8th cycle, further cycles may be allowed for patients who still benefit from the treatment based upon the Investigator's medical judgement and medical monitor approval.

2. STUDY OBJECTIVES

2.1.1.1. PRIMARY OBJECTIVE

- To identify the MTD of MEN1309 when given as an IV infusion on Day 1 of a 21-day cycle in patients affected by CD205-positive solid tumors and NHL.

- To identify the DLT of MEN1309.

2.1.1.2. *SECONDARY OBJECTIVE*

- To assess the toxicity profile of MEN1309.
- To assess the pharmacokinetic (PK) profile after single and repeated doses of MEN1309 following IV administration.
- To determine the immunogenicity of MEN1309.
- To determine the preliminary clinical activity of MEN1309 in the overall treated population and in the Cohort expansion of TNBC patients

2.1.1.3. *EXPLORATORY OBJECTIVE*

- To determine the correlation between free CD205 with the clinical activity of MEN1309.
- To determine the correlation between CD205 expression on formalin-fixed and paraffin-embedded (FFPE) archived tissues samples and/or derived from new tumor biopsies and the clinical activity of MEN1309.
- To determine the deoxyribonucleic acid (DNA) sequence of CD205 at baseline.
- To determine the CD205 expression by flow cytometry on peripheral blood cells at baseline.
- Time course of CEA, CA 15-3 markers in the Expansion Cohort in TNBC patients

3. INVESTIGATIONAL PLAN

3.1.1.1. *OVERALL STUDY DESIGN AND PLAN*

SHUTTLE-01 is an open-label, multicenter, phase I dose escalation study to run in 2 steps.

Step 1 aims to establish the DLT and MTD of MEN1309 in patients with CD205-positive advanced solid tumors with dose escalation starting with 1 single patient per cohort and double dose steps per dose level (Accelerated Titration Design-ATD) until grade ≥ 2 drug-related toxicity is observed in the 21-day period following the first administration of MEN1309.

Upon occurrence of grade ≥ 2 drug-related toxicity, the dose escalation has to follow a modified Fibonacci sequence in which the dose increments become smaller as the dose increases (i.e., dose-increase by 67%, 50%, 40% and 35% of the preceding doses) and a minimum of 3 patients per cohort are to be enrolled, with a minimum 7-day stagger between patients.

Any cohort in which 1 patient experiences a DLT during the DLT assessment window (the 21-day period following the first administration of MEN1309) will be expanded up to 6 patients (with a minimum 24 hours stagger between the 3 additional patients).

Step 2 aims to establish the DLT and MTD of MEN1309 in patients with CD205-positive NHL, following the dose escalation cohorts based upon experience gained during Step 1 in solid tumors.

In both Step 1 and Step 2, if 2 or more patients experience a DLT at any dose level, further enrolment at that dose level and further dose escalation will cease and the previous dose level will be defined as the MTD. However, if ≥ 2 DLTs occur during the dose escalation period, an intermediate dose level can be evaluated prior to defining the previous dose level as MTD.

[figure not shown]
In both Step 1 or Step 2, each dose level escalation (or de-escalation) at the pre-defined dose level of MEN1309 or at any intermediate dose levels will be subject to the assessment of the CRC, which consists of the Principal investigators and the Sponsor's qualified Medical Representatives (and invited experts, when needed).

In addition, the CRC has the duty to drive any adjustment in premedication and concomitant medication. The CRC decisions will be immediately implemented and notified to the CA/EC, when appropriate.

At the time when Step 2 starts, the CRC will include investigators who are treating the NHL patients.

SCHEMATIC DESIGN: Dose Escalation and Cohort Expansion study design (AS EXAMPLE ONLY):

- **Step 1: Solid Tumors**, from 0.05 mg/kg up to MTD and the Expansion Cohort in TNBC
- **Step 2: NHL**, from 0.80 mg/kg (or at lower level) up to MTD

STUDY FLOW-CHART

PROCEDURE	Pre-screening Period Day -112 to Day -28	Screening Visit Day -27 to Day -1	STUDY VISITS							
			Cycle 1			Cycle 2			Cycle 3+	End of Study Visit ^m
			Visit 1 ^l		Visit 2 & 3	Visit 1		Visit 2 & 3		
			Day 1	Days 2-4	Days 8 & 15	Day 1	Days 2-4	Days 8 & 15		
Cohort assignment			X						Same as per Cycle 2	
TLS Risk Assessment ^h			X							
TLS Prophylaxis ⁱ			X			X				
Premedication ^j			X			X				
Study drug administration			X			X				
Adverse events		X	X	X	X	X	X	X		X ^j
Concomitant medications			X	X	X	X	X	X		X
Overall survival ^k										

Abbreviations: ECOG PS = Eastern Cooperative Oncology Group Performance Status; ECG = electrocardiogram; IHC = Immunohistochemistry; NHL = Non-Hodgkin lymphoma; TLS = Tumor lysis syndrome

a = IHC to be analysed locally for enrolment in the Dose-escalation Phase and centrally for enrolment in Expansion Cohort in TNBC.

b = Informed consent to undergo the study procedures, including the performance of the new biopsy, whenever possible.

c = Tumor/NHL assessment will be done, using RECIST v1.1 for solid tumors based on CT scan or MRI and using Cheson Criteria (The Lugano Classification, 2014) for NHL, based on CT/(PET)-CT scans or MRI not older than 2 weeks at Screening Visit, in the last 6 weeks (4+2 weeks) at Visit 1 (Day 1) prior to study drug administration. Images shall be repeated to allow tumor/NHL assessment every other cycle and at the End of Study Visit. Only during the in Expansion Cohort in TNBC population,tumor marker assessment will be done on Day 1 of every other cycle starting from Cycle 1 and at the End of the Study Visit.

d = Ophthalmic or dermatologic visits to be performed and repeated bi-weekly in case of ocular or dermatological events higher than grade 1 during the study treatment period. The frequency of ocular or dermatological events can be increased upon Investigator's judgement.

e = Vital signs to be collected prior to study drug administration, every 15 minutes at Cycle 1 and every 30 minutes starting from Cycle 2 during the first hour of study drug administration and then at every hour until the end of infusion. In case of temporary infusion interruption, vital signs should be collected every 15 minutes until the first hour post-infusion re-start and then every hour until the end of infusion (or until 1-hour after the permanent infusion interruption).

f = 12-lead ECG record to be performed prior to study drug administration and 30 minutes after the end of the infusion; ECG will be also monitored during IV infusion up to 30 minutes after the end of infusion. If ECG monitoring equipment is not available, at Cycle 1 heart rate should be monitored up to 30 minutes after the end of infusion and 12-lead ECG recorded at 30, 60 and 120 minutes during the IV infusion with final 12-lead ECG record at 30 minutes after the end of infusion; starting from Cycle 2, heart rate should be monitored up to 30 minutes after the end of infusion with final 12-lead ECG record at 30 minutes after the end of infusion.

g = See “Blood Samples Flow Chart and PK Blood Samples Flow Chart” (Section 2.3 and Section 2.4) that includes blood sample collection for safety laboratory tests, β -HCG pregnancy test, Anti-HIV Antibodies, Anti-HBcAg antibodies, Anti-HBsAg antibodies, HBV-DNA, HCV-RNA tests, immunogenicity assessment, free CD205 assessment, flow Cytometry for CD205 expression and DNA sequence of CD205 assessment.

h = TLS Risk Assessment according to Investigator’s TLS manual, will be performed ONLY prior to study drug administration at Visit 1 (Day 1) of Cycle 1 (see [Appendix II](#)).

i = TLS prophylaxis should be given every cycle, if applicable (see [Appendix II](#)).

j = Mandatory premedication with an antihistaminic and an antipyretic (as per local practice) and dexamethasone 20 mg will be administered 30 to 60 minutes prior to study drug administration. Starting from Cycle 3, the dose of dexamethasone can be adjusted upon Investigator’s judgement.

k = After the End of Study Visit, all patients evaluable for efficacy will be followed for survival status according to local practice (a visit or a telephone call) every 12 weeks up to a period of 12 months after first treatment administration to the last patient.

l = At Visit 1 of Cycle 1, hospitalisation is required until the completion of study procedures at 48 hours. Patient can remain hospitalised for the completion of the study procedures up to 72 hours. During Cohort Expansion in the TNBC population hospitalization at Cycle 1 is upon investigator judgment up to 24 hours. Starting from Cycle 2, hospitalisation is not mandatory in both Dose-escalation Phase and Expansion Cohort in TNBC, if the patient did not experience any infusion reactions or any adverse events during the administration at Cycle 1.

m = End of Study Visit planned within 6 weeks after the last administered dose or at the time of study withdrawal/treatment discontinuation of study drug.

BLOOD SAMPLES FLOW CHART

PROCEDURE	Pre-screening Period Day -112 to Day -28	Screening Visit Day -27 to Day -1	STUDY VISITS							
			Cycle 1			Cycle 2			Cycle 3+	End of Study Visit
			Visit 1		Visit 2 & 3	Visit 1		Visit 2 & 3		
			Day 1	Days 2-4	Days 8 & 15	Day 1	Days 2-4	Days 8 & 15		
Safety Laboratory Tests (Haematology, Biochemistry, Coagulation) ^a		X	X	X	X ^c	X	X	X ^d	Same as per Cycle 2 ^b	X
β-HCG Pregnancy Test ^a		X	X			X				X
PK Blood sample collection ^b			X	X	X	X	X	X		
Anti-HIV Antibodies, Anti-HBcAg antibodies, Anti-HBsAg antibodies, HBV-DNA, HCV-RNA Tests		X								
Immunogenicity Assessment		X				X				X
Free CD205 Assessment		X				X				X
Flow Cytometry for CD205 expression		X								
DNA sequence of CD205 Assessment ^d		X								

Abbreviations: DNA = deoxyribonucleic acid; HBcAg = hepatitis B core antigen; HBsAg = hepatitis B surface antigen; HBV = hepatitis B virus; HCG = human chorionic gonadotropin; HCV = hepatitis C virus; HIV = human immunodeficiency virus; RNA = ribonucleic acid

a = For a list of all parameters to be analysed, please see **Errore. L'origine riferimento non è stata trovata.** b = Timings of each blood sample collection for PK are listed in the “PK Blood Samples Flow Chart” (Section **Errore. L'origine riferimento non è stata trovata.**). c = Blood sample collection for haematology laboratory test to be repeated at Visit 2 on Day 11 and at Visit 3 on Day 18 of Cycle 1. Starting from Cycle 2, blood sample collection for haematology laboratory test at Day 11 and Day 18 shall be performed if clinically needed.d = For Dose-escalation Phase ONLY.

4. SAFETY ASSESSMENT

Safety and tolerability endpoints will be derived from the following measurements/evaluations:

- Incidence, intensity, CTCAE version 4.03 grading, seriousness, and treatment-causality of Treatment Emergent Adverse Events (TEAEs).
- Frequency of clinically significant abnormalities in:
 - Physical examination and vital signs.
 - Safety laboratory tests.
 - 12-lead ECG record.
 - Urinalysis.

5. STUDY ENDPOINTS

5.1.1.1. PRIMARY ENDPOINT

Identification of MTD, defined as the highest dose level at which no more than 1 of 6 patients experiences a DLT during the DLT assessment window. Identification of DLT, defined as any of the following adverse drug reactions (ADRs) that is assessed during Cycle 1:

- any grade ≥ 3 cardiac toxicity, new segmental wall-motion abnormalities, or cardiac troponin I or T elevation of grade 3 or higher;
- any grade ≥ 3 elevations in total bilirubin, hepatic transaminases, or ALP levels; in patients with baseline grade 2 hepatic transaminase or ALP levels, an elevation to $\geq 10 \times$ ULN is considered a DLT;
- any grade 3 non-haematologic toxicity lasting > 7 days, (excluding diarrhoea/nausea for which no adequate and optimal therapy has been implemented and alopecia);
- any grade 3 vomiting lasting > 3 days despite adequate and optimal therapy;
- any grade ≥ 4 non-haematologic toxicity;
- any grade 4 thrombocytopenia or anaemia;
- any grade 4 neutropenia lasting > 7 days or febrile neutropenia;

- any treatment delay of > 2 weeks because of delayed recovery from toxicity related to MEN1309 (except for alopecia).

Upon the prophylactic use of growth factor support for neutropenia is made mandatory by the CRC, the DLT criterion related to grade 4 neutropenia has changed as follows:

- any grade 4 neutropenia lasting > 5 days or febrile neutropenia despite the use of growth factor support.

Although dose escalation is primarily based on the incidence of DLTs during Cycle 1, toxicities that meet criteria for DLTs and are observed during Cycle 2 or subsequent cycles are also taken into account for the assessment of toxicity and definition of MTD.

5.1.1.2. Secondary Endpoints

Preliminary anti-tumor activity

Step 1 (solid tumors): is assessed in terms of Response Rate (RR), Disease Control Rate (DCR) and duration of response (DOR). RECIST 1.1 assessment is performed using CT scan or MRI of the chest and abdomen (including adrenal glands). Any other areas of disease involvement are additionally investigated based on signs and symptoms of individual patients. For the baseline assessment, CT scan or MRI are performed no more than 6 weeks (4+2 weeks) before the treatment start. Follow-up assessment is performed every other cycle during study treatment (within a window of -7/+3 days of the scheduled date and in any case before the study drug administration of the subsequent Cycle) until objective disease progression as defined by RECIST 1.1 or at the End of Study Visit.

Step 2 (NHL): is assessed in terms of CR, PR and DOR. Cheson Criteria assessment (The Lugano Classification, 2014) is performed using CT/PET-CT scan or MRI of chest and abdomen (including adrenal glands). Any other areas of disease involvement is investigated based on signs and symptoms of individual patients. For the baseline assessment, CT/ PET-CT scan or MRI is performed no more than 6 weeks (4+2 weeks) before the treatment start. Follow-up assessments are performed every other cycle during study treatment (within a window of -7/+3 days of the scheduled date and in any case before the study drug administration of the subsequent Cycle) for a total of 8 cycles or until objective disease progression as defined by Cheson Criteria (The Lugano Classification, 2014) or at the End of Study Visit.

Preliminary clinical efficacy

Overall Survival is defined as the number of days between the first study drug administration and death from any cause. Patients without the event are censored to the last date of follow-up. Progression free survival is defined as the number of days between the first study administration to the date of first documented disease progression, relapse or death from any cause. Responding patients and patients who are lost to follow-up are censored at their last tumor assessment date.

5.1.1.3. *Exploratory endpoints*

To determine the correlation between free CD205 at baseline with clinical activity of MEN1309.

To determine the correlation between CD205 expression and clinical activity of MEN1309. Protein expression will be assessed through IHC centrally evaluated on archived and, when available, new bioptic tissue samples.

To determine the DNA sequence of CD205 at baseline.

To determine CD205 expression by flow cytometry on peripheral blood cells (at baseline).

Time course of CEA, CA15-3 markers in Expansion Cohort in TNBC patients.

5.1.1.4. *Immunogenicity Endpoints*

Incidence of anti-MEN1309 auto-antibodies.

5.1.1.5. *Pharmacokinetic Endpoints*

The following PK variables will be assessed for MEN1309, tAb, DM4 and its metabolite S-methyl-DM4, when applicable: Cmax, tmax, Clast, tlast, Ctrough, ke, t1/2, AUC(0-t), AUC(0-∞), %AUCex, CL, Vss, Vd, AUMC(0-∞), MRT and Ro. PK parameters will be calculated after the first and second infusion of each dose cohort. Cmax and Ctrough will also be obtained after each administration of MEN1309.

5.1.1.6. *Safety Endpoints*

Incidence, intensity, CTCAE version 4.03 grading, seriousness and treatment-causality of TEAEs. Frequency of clinically significant abnormalities in physical examination, safety laboratory tests, urinalysis, vital signs and 12-lead ECG record.

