8.2.4 End of Study

After the End of Study Visit, all patients evaluable for efficacy will be followed for survival status according to local practice (a visit or a telephone call) every 12 weeks up to a period of 12 months after first treatment administration to the last patient.

The study ends 12 months after first treatment administration to the last patient.

All biological samples (including tumor slides and block and excepting safety blood samples) collected along the study will be stored for a maximum of 10 years from the date of the last patient last visit. After 10 years, the samples will be destroyed, or a new IEC/IRB approval and informed consent will be requested to keep the samples for an additional time period.

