9.3 STATISTICAL ANALYSIS

9.3.1 Descriptive statistics

All study variables will be presented by dose-cohort and overall, using the appropriate descriptive statistics according to the variable nature, unless otherwise specified:

- Continuous variables: number of non-missing observations, arithmetic mean, standard deviation (StDev), standard error (SE; for PK variables), minimum, median, maximum (and geometric mean and its 90% confidence interval [CI] for PK variables).
- Categorical variables: number of non-missing observations and column percentages (N, %).

- Time to event variables: number of non-missing observations, number and percentage of censored observations, 1st quartile, median (and its 95% CI), 3rd quartile, Kaplan-Meier survival curves and event rate every two cycles, and at the End of Study Visit and at the End of Study, as appropriate.

The behavior over time of study variables will be summarized by treatment cohort and overall as follows:

- Continuous variables: descriptive statistics for each time point and for the absolute/percentage differences to baseline. For PK variables, only descriptive statistics for each time point will be used.
- Discrete variables: descriptive statistics for each time point and shift tables to baseline.

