9.3.5 Data imputations

Missing values will not be imputed since for every analysis an observed-cases approach will be applied.

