Summary statistics will also include the number and percentage of patients with Normal, Abnormal NCS (Non Clinically Significant) or Abnormal CS (Clinically significant), by parameter and visit. Shift tables will be presented with the counts of individual shifts from each of the reference range categories from baseline to post-dose by laboratory parameter, cohort and visit.

All laboratory data will also be reported in listings.

Previous/ Concomitant medication

All medication taken within 30 days before enrolment and taken during the study will be listed. Medication will be coded using the WHO drug dictionary (version C_DD_Jun2012-WithPrefTerm) and summarised by PT and by anatomical therapeutic chemical (ATC) category level X.

Previous medications are those which start within 30 days prior to enrolment and stopped prior to first dose of study drug. Concomitant medications are those which are started on or after date of first induction, or started prior to induction and stopped after or are ongoing.

The number and percentage of patients of previous and concomitant medication will be tabulated and summarized for concomitant medications.

Any previous and concomitant medication record will also be presented in a listing.

Electrocardiogram (ECG) Evaluations

ECG judgment collected on the eCRF will be summarised descriptively by cohort and visit. Similarly, changes from baseline for each post baseline visit will be summarised.

Vital Signs Evaluations, weight

Vital signs (systolic and diastolic BP (Blood Pressure - mmHg), weight reported in kilograms (kg), heart rate), will be summarised descriptively by cohort and visit. Similarly, changes from baseline will be summarised for all scheduled post baseline visits.

All vital signs parameters will be listed.

Physical Examinations

Physical examination findings (Normal, Abnormal NCS or Abnormal CS) will be summarised using descriptive statistics by Body System, cohort and visit.

Abnormal NCS or Abnormal CS findings on physical examination will be presented in a listing.

Efficacy Analyses

During CRC meeting no efficacy data can be analyzed since efficacy assessment (MRI TC PET scan) will be repeated every 2 cycle.

The efficacy will be evaluated at the end of the study.

Pharmacokinetics Analysis

Pharmacokinetics section will be present upon availability of laboratory data.

Plasma concentrations will be reported for each time point.

PK parameters will be reported with:

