6.1.1.4. DETERMINATION OF SAMPLE SIZE

As first estimation, approximately 122 evaluable patients are expected to be enrolled in the clinical research study: 100 in Step 1 (including 25 patients to be receive MEN1309 in the Expansion Cohort) and 22 in Step 2; however, the total number of evaluable patients depends upon the number of doses and patients by dose cohorts to establish the MTD in Step 1 and Step 2.

It is anticipated that approximately 20% of patients will not pass successfully the Screening Visit. Patients who drop out prior to be evaluable for DLT during the dose escalation will be replaced.

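### The PFS censoring sentence selects patients by response status instead of by absence of an event: it conflicts with the event definition for responders who later progress or die, and gives some event-free patients no censoring time

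*SAP*

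**What the plan says.** SAP 5.1.1.2 gives the event first: "Progression free survival is defined as the number of days between the first study administration to the date of first documented disease progression, relapse or". The list is completed by mortality, whatever its cause. The next sentence is the whole of the censoring rule: "Responding patients and patients who are lost to follow-up are censored at their last tumor assessment date". The protocol has the same two sentences in its synopsis and in 8.5.5.2.

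In the same SAP section, overall survival has a rule built on absence of the event: "Patients without the event are censored to the last date of follow-up".

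Protocol 9.3.1 lists the outputs that depend on censoring: "Time to event variables: number of non-missing observations, number and percentage of censored observations, 1st quartile, median (and its 95% CI), 3rd quartile", followed by Kaplan-Meier curves and event rates. The standard descriptive statistics in SAP 6.1.1.2 cover only continuous and categorical variables. Its efficacy paragraph adds no censoring rule and ends with "The efficacy will be evaluated at the end of the study". Protocol 9.3.3 limits the efficacy analysis to descriptive statistics. Neither document states a PFS event count, median, test or power.

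**The concern.** In a standard PFS analysis a patient is censored because no progression or death has been observed. Response plays no part. This sentence uses response as the criterion, and two things follow.

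First, it is not limited to responders who are still in response and event-free. A responder who later progresses or dies satisfies both sentences, and the text does not say which prevails. If the censoring sentence prevailed, the events removed would be those of responders, censoring would depend on prognosis, and the Kaplan-Meier curve would be too high.

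Second, a patient can be event-free, not a responder and still in contact. No sentence assigns that patient a time, so someone would have to decide the handling after the data are in hand.

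At stake are the PFS event counts, percentage censored, quartiles and curves. The groups are small: results are shown by dose cohort, and the SAP introduction plans 25 patients at the MTD in the TNBC expansion. A few reclassified patients can move such a curve visibly.

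**Working it through.** **Step 1: the two sentences applied to each type of patient.**

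| Patient | Event definition | Censoring sentence | Result |
|---|---|---|---|
| Non-responder (including stable disease) who progresses or dies | event | not named | event |
| Responder, still in response | no event | named | censored |
| Responder who later progresses or dies | event | named | conflict |
| Event-free, lost to follow-up | no event | named | censored |
| Event-free, not responding, still in contact | no event | not named | no time assigned |

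The fourth column is determinate for three of the five types.

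**Step 2: can the last type occur?** Yes:
- Protocol 8.2.3 withdraws patients for DLT, which need not coincide with progression.
- The SAP introduction limits Step 2 treatment to 8 cycles unless an extension is approved.
- Protocol 8.2.4 ends the study 12 months after the last patient's first dose, when some patients may still be stable.
- After the End of Study Visit the protocol schedules contact for survival status only, so a patient can be in contact without being scanned.

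**Step 3: size, by illustration.** There is no plan figure to reproduce. From the documents: scans every 2 cycles, that is 2 × 21 days = 6 weeks; group size 25, as in the TNBC expansion. Assumed, not from the documents:
- R responders, all of whom later progress. For R = 5 the times are weeks 18, 24, 36, 36 and 48.
- 8 stable patients: two progress at each of weeks 12, 18 and 24, and two are event-free at week 30.
- The remaining 25 − 8 − R progress at week 6.

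The product-limit estimate is S(t) = Π(1 − d/n), with d events among n at risk. A responder's last assessment is taken to be the scan that shows progression. For R = 5, to week 24:
- Standard rule: 13/25 × 11/13 × 8/11 × 5/8 = 5/25 = 20.0%, with 23 events in all.
- Responders censored: 13/25 × 11/13 × 9/11 × 6/8 = 27.0%, with 18 events in all. The curve then stays at 27.0%, while the standard curve falls to 6.7% at week 36 and 0% at week 48.
- The two event-free stable patients omitted (n = 23): 11/23 × 9/11 × 6/9 × 3/6 = 3/23 = 13.0%.
- Both at once: 11/23 × 9/11 × 7/9 × 4/6 = 20.3%, so here the two effects nearly cancel.

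Varying R, with the responder times for R = 2 being weeks 18 and 24, and for R = 8 adding weeks 30, 42 and 24 to the five above:

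| R | Standard: events, week-24 PFS | Responders censored: events, week-24 PFS | Event-free stable omitted: week-24 PFS |
|---|---|---|---|
| 2 | 23, 8.0% | 21, 14.4% | 0% |
| 5 | 23, 20.0% | 18, 27.0% | 13.0% |
| 8 | 23, 28.0% | 15, 39.3% | 21.7% |

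**Step 4: effect on the median, also on assumed values.** This is a simulation of 200 patients. Non-responders have exponential PFS with median 2 months. Responders have 1.4 months plus an exponential time with median 6 months, and all of them are censored at the last scan before progression. Median PFS moves from 2.57 to 2.75 months with 20% responders and from 2.96 to 3.37 months with 30% (3.37/2.96 = 1.14, or +14%). With 10% responders it moves from 2.25 to 2.31.

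**The case against.** The strongest reply is that the sentence should be read with the one before it. PFS ends at first documented progression or death, censoring conventionally applies only to patients without an event, and so the responding patients must be those still in response at the cut-off. That is a natural reading. It makes the loss of responders' events a risk of the literal wording, not a certainty. It does not repair the gap for event-free stable patients.

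On that gap, a patient who later progresses or dies has an event date, and Step 1 patients are treated to progression with a scan at the End of Study Visit. The 8-cycle limit applies only to Step 2. A patient no longer scanned could also be treated as lost for progression and censored at the last scan, which is the result one would want. This narrows the gap to patients who are event-free, not responding and still in contact. It does not close it, because the text does not say that these patients count as lost to follow-up.

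A reader might also infer that Protocol 9.3.5 removes these patients, since it says "Missing values will not be imputed since for every analysis an observed-cases approach will be applied". It does not say that: it rules out imputation and is silent on patients whom no censoring category covers. Nor do the documents show that the literal rule would be the one programmed. No programming rule is given, and the SAP's list of tables has only a heading in the available text.

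Finally, the illustrations rest on response rates and medians that the documents do not contain, and 200 patients exceeds the planned 122. In groups of 25, under the same simulation assumptions, the shift in the median is smaller than the median's own sampling standard deviation at response rates of 10% to 30%. This stands, and it limits the practical weight of the point.

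**Conclusion.** The sentence is wrong as written and should be corrected, with limited consequence. Followed literally, it gives wrong PFS event counts and Kaplan-Meier estimates for responders who later progress or die, and it leaves one foreseeable group without a time.

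A reader might infer that reported PFS will be biased upward. The documents do not support that. Censoring responders' events would raise PFS, leaving out event-free stable patients would lower it, and the text settles neither. In the example with 5 responders the week-24 estimate ranges from 13.0% to 27.0% around 20.0%, depending only on how the wording is resolved. That range depends on the assumed data and is not a prediction for this trial.

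PFS is a secondary endpoint reported descriptively, with no test, power calculation or decision rule attached. Identification of the MTD and DLT is unaffected.

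**What to change.** In SAP 5.1.1.2, before database lock, replace the censoring sentence with: *Patients without documented progression, relapse or death are censored at their last evaluable tumor assessment (Day 1 if none), whatever their best response; responders who later progress or die count as events.*

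This brings PFS into line with the overall survival rule in the same section and gives every patient in the Step 1 table exactly one outcome. The cost is one sentence in the SAP. No new data, visits or assessments are needed.
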